11. SAFETY

Safety endpoints will be analyzed using the Safety population and will be summarized descriptively as described in section **Error! Reference source not found.** Safety data will be summarized separately for Part 1 (SAD) and Part 2(MAD).

11.1 Adverse Events

All AEs including will be coded using latest MedDRA version. All AE summaries will be restricted to TEAEs only. AEs will be grouped by system organ class (SOC) and preferred term (PT) and summarized, by actual treatment group and overall. Summary tables will include the number of participants (%) experiencing an event and the number of events. Participants will be counted only once for each SOC and PT level; they will be sorted alphabetically and for PT tables only, they will be ordered with the highest first (categorical descriptive analysis).

For food effect cohort, an adverse event starting in one period and continuing into the next period is counted only in the onset period.

Assigned treatment	Definition
Treatment Period 1 (Fasting)	AE start date/time is on or after the dose date/time of treatment received in Period 1 and prior to the date/time of treatment received in period 2 (fed period) no matter when AE stops.
Treatment Period 2 (Fed)	AE start date/time is on or after the dose date/time of treatment received in Period 2 until the end of study.

For Part 1 (SAD) Cohort S3 food effect arm, TEAE will be further assigned to S3/Fasted (period 1) or S3/Fed (period 2) by using period 2 start date and TEAE's that start post first study drug administration of period 2 (Fed) will not be attributed to treatment during period 1 (Fasted). TEAE's that start post first study drug administration of period 1, but prior to first study drug administration of period 2, will be attributed to period 1 only. TEAEs that start post first study drug administration of period 1 (Fasted) and ongoing will be attributed to Onset period only

The TEAE summaries will include:

- Overall summary of TEAEs.
- TEAE summary by SOC and PT.
- TEAE summary of serious events by SOC and PT.
- TEAE summary by SOC, PT and Severity.
- TEAE summary by SOC, PT and relationship to study drug.
- TEAE summary of events leading to the study drug discontinuation by SOC and PT.
- Overall Frequency of TEAE by PT.
- Overall Frequency of related TEAE by PT.

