2.1.1 Part 1: SAD is the single-dose regimen and Fasted- Fed Crossover

Approximately 40 healthy male or female subjects will be enrolled in 1 of 5 single-dose cohorts (designated as S1 through S5, respectively) in an ascending fashion. An optional Cohort 3a may be added in parallel to SC3 for additional safety and tolerability evaluation. Cohort S3a dose level will be consistent with Cohort S3 (45 mg planned) in a fasted condition only and without lumbar puncture, aligned with other SAD cohorts. Each cohort will consist of 8 subjects randomized to CVN766 or placebo, whereby 6 subjects will receive a single oral dose of CVN766 suspension, and 2 subjects will receive a matching placebo suspension under overnight fasted conditions. Sentinel dosing (1 subject to receive CVN766 and 1 subject to receive placebo) will be used in each cohort to ensure adequate safety and tolerability evaluation prior to administering CVN766 or placebo to the remainder of the subjects within the cohort. The planned dose levels will be 5, 15, 45, 125, and 250 mg CVN766. Each following dose level may be higher, lower, or remain the same as the preceding cohort. Additional cohort(s) may be added if deemed necessary by the SRG to fully characterize the safety and tolerability of CVN766. To assess the effect of food on CVN766 bioavailability in suspension formulation, the single-dose administration will be repeated in a single cohort (S3) after ingestion of a standardized high-fat, high-calorie meal. Once the safety of the S3 cohort dose level has been assessed, the S3 cohort subjects will return to the clinic (no sooner than 14 days after their prior dose, or at least 4 half-lives, has lapsed based on preliminary PK data, whichever is longer). They will receive the same dose as before, administered after ingesting a standardized breakfast. Subjects will finish at least approximately 85% of their breakfast within 30 minutes and receive an investigational product 30 minutes (\pm 5 minutes) after beginning the meal. Sentinel dosing will not be required for subjects returning to the clinic for the fed regimen. If the CVN766 PK parameters in the fasted S3 cohort reveal poor absorption with inconclusive results, the fed cohort will be deferred until a higher dose level.

[figure not shown]
On Day 1, subjects will undergo safety monitoring and PK sampling from blood plasma through 72 hours post-dose and, for cohort S3 (fasted) only, from CSF via lumbar puncture at 3 hours post-dose

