2.3 Endpoints

Primary endpoint(s)

The primary endpoints of this study will be the following:

- Percentage of subjects who experience at least one treatment-emergent adverse event (TEAE)
- Percentage of subjects with abnormal and clinically significant (CS) safety laboratory test results at least once post-dose
- Percentage of subjects with abnormal and CS electrocardiogram (ECG) test results at least once post-dose
- Percentage of subjects with abnormal and CS vital sign measurements at least once post dose

Secondary endpoints(s)

- Single-dose plasma PK parameters of CVN766 including time to maximum plasma concentration (T_{max}), area under the plasma concentration-time curve from time 0 to 24 (AUC_{24}) and time 0 to infinity (AUC_{inf}), and terminal elimination half-life ($t_{1/2z}$) Multiple-dose plasma PK parameters of CVN766 including C_{min} , C_{trough} , C_{max} , AUC from time 0 to the end of dosing interval (AUC_t), terminal elimination half-life ($t_{1/2z}$), accumulation ratio (R_{acc}), time to steady-state ($T_{ss,max}$), steady-state C_{max} ($C_{max,ss}$), and steady-state C_{min} ($C_{min,ss}$) Single-dose and multiple-dose CSF concentrations and CSF: plasma ratios of CVN766

Other endpoints(s)

- Change from baseline in safety laboratory and ECG test results and vital signs.
- Additional plasma PK parameters of CVN766: CL/F or CL/F_{ss} and Vz/F or Vz/F_{ss}

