- **Concomitant Medications:** Concomitant medications are defined as any medication (other than the study drug) that was used at least once after the first administration of the study drug.

Medications that were stopped on the same date as the first study drug administration will be defined as concomitant medications. If a clear determination cannot be made (partial medication end dates) the medication will be classified as concomitant

- Treatment Emergent Adverse Events (TEAEs): are defined as adverse events that occurred within 30 days (onset date – last date of dose + 1 ≤ 30) after study drug administration.

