- Screening Failures (Listing 16.2.4.7 only)

MAD

- Cohort 1/ CVN766 45 mg
 - Cohort 1/ Placebo
 - Cohort 2/ CVN766 125 mg
 - Cohort 2/ Placebo
 - Cohort 3/ CVN766 250 mg
 - Cohort 3/ Placebo
- **Names of visits**
 - **SAD Cohorts 1, 2, 3a, 4, 5.**
 - Visit 1 = Screening
 - Visit 2 = Day -1
 - Visit 3 = Day 1
 - Visit 4 = Day 2
 - Visit 5 = Day 3
 - Visit 6 = Day 4 / Discharge
 - Visit 7 = Day 8 / Outpatient Visit
 - Visit 8 = Day 14 / Follow up / Early Termination
 - **SAD Cohorts 3**
 - Visit 1 = Screening (Listing only)
 - Visit 2 = Day -1
 - Visit 3 = Day 1
 - Visit 4 = Day 2
 - Visit 5 = Day 3

- Visit 6 = Day 4 / Discharge Day
- Visit 7 = Day 8
- Visit 8 = Day 21
- Visit 9 = Day 22
- Visit 10 = Day 23
- Visit 11 = Day 24
- Visit 12 = Day 28 / Discharge
- Visit 13 = Day 42 / Follow up / Early Termination
- **MAD Cohorts 1, 2, 3**
 - Visit 1 = Screening (Listing only)
 - Visit 2 = Day -1
 - Visit 3 = Day 1
 - Visit 4 = Day 2
 - Visit 5 = Day 3
 - Visit 6 = Day 4
 - Visit 7 = Day 5
 - Visit 8 = Day 6
 - Visit 9 = Day 7
 - Visit 10 = Day 8
 - Visit 11 = Day 9/ Inpatient discharge
 - Visit 12 = Day 10/ Outpatient visit
 - Visit 13 = Day 14/ Outpatient visit
 - Visit 14 = Day 21/ Follow up/ Early Termination

Table 14.1.1.1 Summary of Participant Enrolment and Disposition SAD (Safety Population)

	CVN766 5 mg (N=xx)	CVN766 15 mg (N=xx)	Etc.	Overall (N=xx)
Number of Participants who Completed the Study	xx (xx.x%)	xx (xx.x%)	xx (xx.x%)	xx (xx.x%)
Number of Participants who did not Complete the Study	xx (xx.x%)	xx (xx.x%)	xx (xx.x%)	xx (xx.x%)
Primary Reason for Non-Completion				
Adverse Event	xx (xx.x%)	xx (xx.x%)	xx (xx.x%)	xx (xx.x%)
Death	xx (xx.x%)	xx (xx.x%)	xx (xx.x%)	xx (xx.x%)
Failure to Meet Randomization Criteria	xx (xx.x%)	xx (xx.x%)	xx (xx.x%)	xx (xx.x%)
Lack of Efficacy	xx (xx.x%)	xx (xx.x%)	xx (xx.x%)	xx (xx.x%)
Lost to Follow Up	xx (xx.x%)	xx (xx.x%)	xx (xx.x%)	xx (xx.x%)
Non-compliance with Study Drug	xx (xx.x%)	xx (xx.x%)	xx (xx.x%)	xx (xx.x%)
Physician Decision	xx (xx.x%)	xx (xx.x%)	xx (xx.x%)	xx (xx.x%)
Pregnancy	xx (xx.x%)	xx (xx.x%)	xx (xx.x%)	xx (xx.x%)
Protocol Deviation	xx (xx.x%)	xx (xx.x%)	xx (xx.x%)	xx (xx.x%)
Screen Failure	xx (xx.x%)	xx (xx.x%)	xx (xx.x%)	xx (xx.x%)
Site Terminated by Sponsor	xx (xx.x%)	xx (xx.x%)	xx (xx.x%)	xx (xx.x%)
Study Terminated by Sponsor	xx (xx.x%)	xx (xx.x%)	xx (xx.x%)	xx (xx.x%)
Technical Problems	xx (xx.x%)	xx (xx.x%)	xx (xx.x%)	xx (xx.x%)

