If a participant has multiple occurrences of a concomitant medication, the participant is presented only once in the participant count (n) column for a given ATC and PT. Occurrences are counted each time in the mentions/occurrence (m) column.

Percentages are calculated (the denominator used for the calculation) based on the number of participants in the safety population in each treatment group (N).

World Health Organization-Drug Dictionary (WHO-DD) Version xx, YYYY

Programing Note:

Add following treatment columns;
 CVN766 5 mg, CVN766 15 mg, CVN766 45 mg(Fasted), CVN766 45 mg(Fed) CVN766 125 mg, CVN766 250 mg, Overall CVN766, Overall Placebo, Placebo (Fed) and Overall
 Overall CVN766 will not contain CVN766 45 mg(Fed)
 Overall Placebo will not contain Placebo (Fed) from S3 Cohort.

Table 14.3.2.2 Summary of Concomitant Medications MAD (Safety Population)

Programing Note:
Same as Table 14.3.1.1
Source: Listing 16.2.10.2.2
Add following treatment columns;
CVN766 45 mg, CVN766 125 mg, CVN766 250 mg, Overall CVN766, Overall Placebo and Overall.

Table 14.3.3.1.1 Summary of Overall Treatment Emergent Adverse Events SAD (Safety Population)

	CVN766 5 mg (N=xx) n (%) m	etc.	Overall (N=xx) n (%) m
Number of Participants Reporting at least one:			
TEAE	xx (xx.x%) xx	xx (xx.x%) xx	xx (xx.x%) xx
Severe TEAE	xx (xx.x%) xx	xx (xx.x%) xx	xx (xx.x%) xx
Treatment Related TEAE	xx (xx.x%) xx	xx (xx.x%) xx	xx (xx.x%) xx
Serious TEAE	xx (xx.x%) xx	xx (xx.x%) xx	xx (xx.x%) xx
TEAE leading to study drug withdrawal[1]	xx (xx.x%) xx	xx (xx.x%) xx	xx (xx.x%) xx
TEAE leading to discontinuation from study	xx (xx.x%) xx	xx (xx.x%) xx	xx (xx.x%) xx
Life threatening TEAE	xx (xx.x%) xx	xx (xx.x%) xx	xx (xx.x%) xx
TEAE leading to death	xx (xx.x%) xx	xx (xx.x%) xx	xx (xx.x%) xx

Source: Listing 16.2.7.1.1

Treatment Emergent Adverse Events (TEAEs) are defined as adverse events that occurred following the first administration of study medication. If a participant has multiple occurrences of a TEAE, the participant is presented only once in the Participant count (n) column for a given System Organ Class and Preferred Term. Occurrences are counted each time in the mentions/Occurrence (m) column.

Percentages are calculated (the denominator used for the calculation) based on the number of participants in the safety population in each treatment group (N).

[1]Action taken = drug withdrawn

Medical Dictionary for Regulatory Activities (MedDRA) Version xx.x

Programing Note:

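### SAD TEAE percentages set columns with about 13 days of follow-up (S1, S2, S4, S5) beside 45 mg columns with about 20 (S3 Fasted) and 21 days (S3 Fed), so they are not comparable across dose without a common window

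*SAP*

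**What the plan says.** The first primary endpoint in SAP section 2.3 is the percentage of subjects with at least one TEAE. The footnotes to the mock TEAE tables take the number of safety-population participants in each column as denominator, not time at risk.

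For the food-effect cohort, section 11.1 assigns events by period. A Period 1 (fasted) event starts on or after the first dose and "prior to the date/time of treatment received in period 2 (fed period) no matter when AE stops". A Period 2 (fed) event is one whose "AE start date/time is on or after the dose date/time of treatment received in Period 2 until the end of study". Neither period is capped at a fixed number of days.

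The visit lists in the General Comments to the mock tables end SAD cohorts 1, 2, 3a, 4 and 5 at "Visit 8 = Day 14 / Follow up / Early Termination". Cohort 3 has visits on Days 1, 2, 3, 4 and 8, then on Days 21, 22, 23, 24 and 28, and ends at "Visit 13 = Day 42 / Follow up / Early Termination". Section 2.1.1 requires only that the fed dose come "no sooner than 14 days after their prior dose", or at least 4 half-lives after it if that is longer.

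Section 3.2 says TEAEs "are defined as adverse events that occurred within 30 days" after study drug administration. The mock TEAE tables instead define them as events after the first administration, with no upper limit.

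Section 3.7 gives S3 Fed its own placebo column and keeps both fed groups out of the pooled columns. S3 Fasted and its placebo participants are in the pooled columns.

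**The concern.** A percentage with at least one event can only rise with observation time. The SAD tables put the dose levels side by side, and reading tolerability across them is the study's primary purpose. If the middle dose is observed for longer than the doses on either side, background events alone can raise its percentage. This could be mistaken for a feature of the 45 mg dose or of the fed state. Nothing in the SAP offsets the difference: there is no common window, no exposure adjustment and no footnote on follow-up time. What is at stake is the descriptive reading of the dose pattern. No test or error rate is involved.

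**Working it through.** The SAP states no TEAE rate or follow-up length to reproduce, so the check starts from its visit lists and attribution rule.

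**Ascertainment windows, if events are collected only to the last visit**

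- S1, S2, S4, S5: dose on Day 1, last visit Day 14, so 14 − 1 = 13 days.
- S3 Fasted: Day 1 to the fed dose. Day 21 is inferred as the fed dosing day, because Days 21, 22, 23, 24 and 28 fit 0, 24, 48 and 72 hours and 7 days after a Day 21 dose. This gives 21 − 1 = 20 days, and 20/13 = 1.54.
- S3 Fed: Day 21 to Day 42, so 42 − 21 = 21 days, and 21/13 = 1.62.
- If the fed dose were on Day 22, the two windows would be 21 and 20 days.

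**Does the 30-day rule equalise them?** The rule (onset date − last dose date + 1 ≤ 30) allows onset up to 29 days after a dose. That exceeds 13, 20 and 21 days, so it truncates none of the windows.

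**Expected percentages with no drug effect, constant hazard.** Let p be the 13-day background risk (an assumption, varied). Then P(T) = 1 − (1 − p)^(T/13).

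| Assumed p (13 days) | S3 Fasted (20 days) | S3 Fed (21 days) | Expected participants of 6 (13 / 20 / 21 days) |
|---|---|---|---|
| 20% | 29.1% | 30.3% | 1.20 / 1.74 / 1.82 |
| 30% | 42.2% | 43.8% | 1.80 / 2.53 / 2.63 |
| 50% | 65.6% | 67.4% | 3.00 / 3.93 / 4.04 |

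For example, 1 − 0.70^(20/13) = 0.422.

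**Early clustering.** Let H = −ln(1 − p), put a share s of H in the first 4 days, and spread the rest at the constant rate (1 − s)H/9 from day 4 onward. Then P(T) = 1 − exp{−[sH + (1 − s)H(T − 4)/9]}. At p = 30%:

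- s = 75%: 34.7% (S3 Fasted) and 35.3% (S3 Fed).
- s = 90%: 31.9% and 32.2%.

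At p = 30% the excess therefore runs from 6 × (0.319 − 0.30) = 0.1 to 6 × (0.438 − 0.30) = 0.8 of a participant.

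**Chance of a visible difference.** With exact binomials, 6 against 6 participants, p = 30% and a constant hazard, S3 Fasted shows a higher count than a given 13-day cohort with probability 56%, an equal count with 21% and a lower count with 23%.

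**If the other cohorts were followed for the full 30-day window (29 days after dose).** With an assumed 29-day risk of 30%, S3 Fasted, still cut off at the fed dose, would be expected at 1 − 0.70^(20/29) = 21.8%. The bias reverses.

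**Pooled columns, p = 30%, constant hazard.** There are 5 × 6 = 30 active and 5 × 2 = 10 placebo participants.

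- Overall CVN766: (24 × 0.300 + 6 × 0.422)/30 = 32.4%.
- Overall Placebo: (8 × 0.300 + 2 × 0.422)/10 = 32.4%.

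S3 is one fifth of each, so this contrast is balanced. S3 Fasted against Overall Placebo is not: 42.2% against 32.4%.

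**The case against.** The strongest objection is that neither direction nor size is fixed by the documents. How adverse events are collected between visits and after the last one is left to the protocol, which is not shown, and the bias can run either way. That stands. A reader might infer that the 45 mg columns will show more TEAEs even if the drug does nothing, or that a true rise at 125 and 250 mg would be masked. The SAP supports neither. The excess is an expectation under one collection rule, and no masking has been demonstrated.

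The 20-day fasted window is also an inference from visit labels, while the text sets only a 14-day minimum. At a 14-day interval S3 Fasted would be expected at 1 − 0.70^(14/13) = 31.9% against 30%, so almost all of its excess disappears. S3 Fed would keep its excess if follow-up still ran 21 days after the fed dose.

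Size is limited too. After a single dose, early clustering is plausible, and it shrinks the effect to about 2 to 5 points at a 30% base rate. One participant in 6 is 16.7 points, so chance differences will usually be larger than the bias.

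Two contrasts are protected. S3 Fed has Placebo (Fed), observed over the same window, and the pooled active and placebo columns carry S3 in equal proportion. The tables also split TEAEs by relationship, and the listings give onset times.

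Finally, S3 Fasted differs from the other cohorts by a lumbar puncture at 3 hours, which no common time window removes. Optional cohort 3a (45 mg fasted, last visit Day 14) could dilute the difference, but the SAP does not say which column it enters. If it were pooled with S3 Fasted, the 42.2% would become (6 × 0.300 + 6 × 0.422)/12 = 36.1%.

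These points reduce the size and remove any claim of direction. They do not make the columns comparable.

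**Conclusion.** The unequal windows follow from the SAP's own attribution rule and visit lists, and nothing in the plan equalises them. The 45 mg TEAE percentages are therefore not directly comparable with those of the other SAD doses, and S3 Fasted is not directly comparable with Overall Placebo.

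If events are collected only to the last visit, the 45 mg columns are inflated in expectation. At an assumed 30% 13-day risk they would stand at about 42 to 44% under a constant hazard, or 32 to 35% if 75 to 90% of the 13-day hazard falls in the first 4 days. This rests on a Day 21 fed dose and 6 active participants per column. If the other cohorts are followed for the full 30 days, S3 Fasted is instead too low.

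The effect is modest and bears only on descriptive interpretation. It is worth correcting because the correction costs almost nothing.

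**What to change.** Keep the all-TEAE row as planned, so that no event leaves the main count of a first-in-human study. Then:

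1. In the SAD overall TEAE summary and the SOC/PT summary, add a row or companion table counting TEAEs with onset within 13 days after the dose of that period, for every column including S3 Fasted, S3 Fed and both placebo columns. The window fits inside Period 1 even at the 14-day minimum interval, and inside Period 2 by the visit list (Day 21 + 13 = Day 34, before Day 42).
2. State in section 11.1 that comparisons across dose, and of S3 Fed with other doses, are read from this common window.
3. Footnote the follow-up time of each column.

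Under no drug effect and the same background hazard after each dose, every column then has the same expected percentage (30% in the example, instead of 30, 42.2 and 43.8%).

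The cost is one sentence, one dataset flag and one extra row or table, using onset dates that the AE listing already carries. One weakness remains: S3 Fasted has no Day 14 visit, so onset dates between Day 8 and Day 21 rely on recall at the next visit.

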5. PARTICIPANT DISPOSITION AND ANALYSIS POPULATIONS

Participant disposition and analysis population analysis will be based on Safety population. Participant disposition and analysis populations will be summarized descriptively as described in section 3.1 (categorical descriptive analysis).

Participant Disposition

Participant disposition will include the number of participants who completed the treatment/study as planned, participants withdrawn from the treatment /study, as well as the primary reason for early termination. Participant disposition will be summarized descriptively.

Analysis Populations

The number of participants included in each study populations will be summarized descriptively.

In addition, the inclusion of each participant into/from each of the defined analysis populations will be presented in the by-participant data listings.

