14.3.3.5.2	Summary of Treatment Emergent Adverse Events by SOC, PT and Relationship MAD	Safety
14.3.3.6.1	Summary of TEAE leading to the study discontinuation by SOC and PT SAD	Safety
14.3.3.6.2	Summary of TEAE leading to the study discontinuation by SOC and PT MAD	Safety
14.3.3.7.1	Summary of Overall Frequency of TEAE by PT SAD	Safety
14.3.3.7.2	Summary of Overall Frequency of TEAE by PT MAD	Safety
14.3.3.8.1	Summary of Overall Frequency of Related TEAE by PT SAD	Safety
14.3.3.8.2	Summary of Overall Frequency of Related TEAE by PT MAD	Safety
14.3.4	Laboratory Parameters	
14.3.4.1.1.1	Summary of Hematology & Coagulation SAD	Safety
14.3.4.1.1.2	Summary of Hematology & Coagulation MAD	Safety
14.3.4.1.2.1	Summary of Hematology & Coagulation Shifts from Baseline SAD	Safety
14.3.4.1.2.2	Summary of Hematology & Coagulation Shifts from Baseline MAD	Safety
14.3.4.2.1.1	Summary of Serum Chemistry SAD	Safety
14.3.4.2.1.2	Summary of Serum Chemistry MAD	Safety
14.3.4.2.2.1	Summary of Serum Chemistry Shifts from Baseline SAD	Safety
14.3.4.2.2.2	Summary of Serum Chemistry Shifts from Baseline MAD	Safety
14.3.4.3.1	Summary of Urinalysis SAD	Safety
14.3.4.3.2	Summary of Urinalysis MAD	Safety
14.3.5	Other Safety	
14.3.5.1.1	Summary of Vital Signs SAD	Safety
14.3.5.1.2	Summary of Vital Signs MAD	Safety
14.3.5.2.1	Summary of Orthostatic Vital Signs SAD	Safety
14.3.5.2.2	Summary of Orthostatic Vital Signs MAD	Safety
14.3.5.3.1	Categorical Tabulation of Orthostatic Vital Signs SAD	Safety
14.3.5.3.2	Categorical Tabulation of Orthostatic Vital Signs MAD	Safety
14.3.5.4.1.1	Summary of 12-Lead ECG SAD	Safety
14.3.5.4.1.2	Summary of 12-Lead ECG MAD	Safety
14.3.5.4.2.1	Summary of 12-Lead ECG Interpretation SAD	Safety
14.3.5.4.2.2	Summary of 12-Lead ECG Interpretation MAD	Safety

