System Organ Class (SOC) Preferred Term (PT) Relationship	CVN766 5 mg (N=xx) n (%) m	etc.	Overall (N=xx) n (%) m
Participants with at least one TEAE	xx (xx.x%) xx	xx (xx.x%) xx	xx (xx.x%) xx
Not Related	xx (xx.x%) xx	xx (xx.x%) xx	xx (xx.x%) xx
Related	xx (xx.x%) xx	xx (xx.x%) xx	xx (xx.x%) xx
SOC1	xx (xx.x%) xx	xx (xx.x%) xx	xx (xx.x%) xx
Not Related	xx (xx.x%) xx	xx (xx.x%) xx	xx (xx.x%) xx
Related	xx (xx.x%) xx	xx (xx.x%) xx	xx (xx.x%) xx
PT1	xx (xx.x%) xx	xx (xx.x%) xx	xx (xx.x%) xx
Not Related	xx (xx.x%) xx	xx (xx.x%) xx	xx (xx.x%) xx
Related	xx (xx.x%) xx	xx (xx.x%) xx	xx (xx.x%) xx
....			

Source: Listing 16.2.7.1.1

Treatment Emergent Adverse Events (TEAEs) are defined as adverse events that occurred following the first administration of study medication. If a participant has multiple occurrences of a TEAE, the participant is presented only once in the Participant count (n) column for a given System Organ Class and Preferred Term. Occurrences are counted each time in the mentions/Occurrence (M) column. SOC / PTs will be presented in decreasing order of 'overall' column.

Percentages are calculated (the denominator used for the calculation) based on the number of participants in the safety population in each treatment group (N).

Medical Dictionary for Regulatory Activities (MedDRA) Version xx.x

Programing Note:

Add following treatment columns;
 CVN766 5 mg, CVN766 15 mg, CVN766 45 mg(Fasted), CVN766 45 mg(Fed), CVN766 125 mg, CVN766 250 mg, Overall CVN766, Overall Placebo Placebo(Fed) and Overall
 Overall CVN766 will not contain CVN766 45 mg(Fed)
 Overall Placebo will not contain Placebo (Fed) from S3 Cohort

Table 14.3.3.5.2 Summary of Treatment Emergent Adverse Events by System Organ Class, Preferred Term and Relationship MAD (Safety Population)

Programing Note:
Same as Table 14.3.3.5.1
Source: Listing 16.2.7.1.2
Add following treatment columns;
CVN766 45 mg, CVN766 125 mg, CVN766 250 mg, Overall CVN766, Overall Placebo and Overall.

Table 14.3.3.6.1 Summary of TEAE leading to the study discontinuation by SOC and PT SAD (Safety Population)

System Organ Class (SOC) Preferred Term (PT)	CVN766 5 mg (N=xx) n (%) m	etc.	Overall (N=xx) n (%) m
Participants with at least one TEAE Leading to Study Discontinuation	xx (xx.x%) xx	xx (xx.x%) xx	xx (xx.x%) xx
SOC1	xx (xx.x%) xx	xx (xx.x%) xx	xx (xx.x%) xx
PT1	xx (xx.x%) xx	xx (xx.x%) xx	xx (xx.x%) xx
...			
SOC2	xx (xx.x%) xx	xx (xx.x%) xx	xx (xx.x%) xx

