PT1	xx (xx.x%) xx	xx (xx.x%) xx	xx (xx.x%) xx
PT2	xx (xx.x%) xx	xx (xx.x%) xx	xx (xx.x%) xx
PT3	xx (xx.x%) xx	xx (xx.x%) xx	xx (xx.x%) xx
PT4	xx (xx.x%) xx	xx (xx.x%) xx	xx (xx.x%) xx
...			

Source: Listing 16.2.7.1.1

Treatment Emergent Adverse Events (TEAEs) are defined as adverse events that occurred following the first administration of study medication. If a participant has multiple occurrences of a TEAE, the participant is presented only once in the Participant count (n) column for a given System Organ Class and Preferred Term. Occurrences are counted each time in the mentions/Occurrence (M) column. SOC / PTs will be presented in decreasing order of 'overall' column.

Percentages are calculated (the denominator used for the calculation) based on the number of participants in the safety population in each treatment group (N).

Medical Dictionary for Regulatory Activities (MedDRA) Version xx.x

Programing Note:

Add following treatment columns;
 CVN766 5 mg, CVN766 15 mg, CVN766 45 mg (Fasted), CVN766 45 mg (Fed), CVN766 125 mg, CVN766 250 mg, Overall CVN766, Overall Placebo Placebo (Fed) and Overall
 Overall CVN766 will not contain CVN766 45 mg (Fed)
 Overall Placebo will not contain Placebo (Fed) from S3 Cohort

Table 14.3.3.6.2 Summary of TEAE leading to the study discontinuation by SOC and PT MAD (Safety Population)

*Programing Note:
Same as Table 14.3.3.6.1
Source: Listing 16.2.7.1.2
Add following treatment columns;
CVN766 45 mg, CVN766 125 mg, CVN766 250 mg, Overall CVN766, Overall Placebo and Overall.*

Table 14.3.3.7.1 Summary of Overall Frequency of TEAE by PT SAD (Safety Population)

Preferred Terms (PTs)	CVN766 5 mg	etc.	Overall
	(N=xx) n (%) m		(N=xx) n (%) m
Participants with at least one TEAE	xx (xx.x%) xx	xx (xx.x%) xx	xx (xx.x%) xx
PT1	xx (xx.x%) xx	xx (xx.x%) xx	xx (xx.x%) xx
PT2	xx (xx.x%) xx	xx (xx.x%) xx	xx (xx.x%) xx
PT3	xx (xx.x%) xx	xx (xx.x%) xx	xx (xx.x%) xx
PT4	xx (xx.x%) xx	xx (xx.x%) xx	xx (xx.x%) xx
PT5	xx (xx.x%) xx	xx (xx.x%) xx	xx (xx.x%) xx
.....			
....			

Source: Listing 16.2.7.1.1

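### The SOC/PT table for TEAEs leading to study-drug discontinuation, planned in SAP section 11.1, is titled and shelled as study discontinuation, and the disposition shells likewise omit the treatment status named in section 5

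*SAP*

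**What the plan says.** Section 11.1 of the SAP lists eight TEAE summaries. The sixth is a "TEAE summary of events leading to the study drug discontinuation by SOC and PT".

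The section 14 table list gives the corresponding MAD table as "Summary of TEAE leading to the study discontinuation by SOC and PT MAD", with a matching SAD title. In the mock shell for Table 14.3.3.6.1 the header row reads "Participants with at least one TEAE Leading to Study Discontinuation". The MAD shell is specified as "Same as Table 14.3.3.6.1", so it inherits that row.

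The shell for Table 14.3.3.1.1, the overall TEAE summary, has a row labelled "TEAE leading to study drug withdrawal[1" with the footnote "1]Action taken = drug withdrawn". Directly below it is a separate row for TEAEs that led to leaving the study. The MAD version, 14.3.3.1.2, uses the same rows.

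On disposition, section 5 says the summary will cover "participants who completed the treatment/study as planned, participants withdrawn from the treatment /study", plus the primary reason for early termination. The shell for Table 14.1.1.1 has a row for completing the study, a row "Number of Participants who did not Complete the Study", and reasons for non-completion. The MAD shell copies it.

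**The concern.** The text and the shells name two different events. A programmer will normally build from the shell. The SOC/PT summary that section 11.1 describes would then not be produced, and a table of something else would stand in its slot. Section 12, which lists changes to the planned analysis, records no decision to switch.

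Safety and tolerability by dose is the primary objective. In an ascending-dose study, the type of event that ended dosing at each dose level is one of the tolerability results a reader looks for in a summary table. If stopping drug and leaving the study can come apart, neither the AE-by-term discontinuation table nor the disposition table will show it.

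**Working it through.** No sample-size or power figure is involved, so the check sets the passages side by side.

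**1. Are the two terms interchangeable in this SAP?** No.
- Table 14.3.3.1.1 gives each event its own row, and derives the drug row from the recorded action taken.
- AE listing 16.2.7.1.1 has one column for action taken and another for whether the participant discontinued because of the AE. The MAD listing copies it.

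**2. Is the section 11.1 summary produced under another number?** No. The eight summaries in section 11.1 correspond in order to Tables 14.3.3.1 to 14.3.3.8. The sixth falls on 14.3.3.6, and no other table breaks discontinuations down by SOC and PT.

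**3. Is treatment completion summarised elsewhere?** No. Section 8 presents exposure in by-participant listings only, and section 14 contains no exposure table. The disposition shells stop at study completion.

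**4. Where can the two events differ?**
- MAD participants are dosed daily for 7 days, and the visit schedule in the mock-table comments runs to a Day 21 follow-up. Stopping drug while remaining in the study is therefore possible on the schedule.
- SAD cohorts other than S3 receive one dose, so there is no later dose to stop.

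**5. What would each output show?** Take one active participant in one MAD cohort who stops drug for an AE, stays in the study and is recorded as completing it. This is an assumption, not something the SAP states. Inputs from sections 2.1.2 and 2.5: 6 active participants per cohort and 3 cohorts, so 3 × 6 = 18 active in all.

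| Output | Result for this participant |
|---|---|
| 14.3.3.1.2, drug-withdrawal row | 1/6 = 16.7% of the cohort's active arm; 1/18 = 5.6% of Overall CVN766 |
| 14.3.3.1.2, study-discontinuation row | 0 |
| 14.3.3.2.2, general SOC/PT table | AE counted under its SOC and PT, not marked as having stopped drug |
| 14.3.3.6.2, as shelled | 0 |
| 14.1.1.2, as shelled | Counted as completing the study |
| Listing 16.2.7.1.2 | AE term and action taken both shown |

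The count survives in a summary table. The link between the count and the SOC/PT survives only in the listing.

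**The case against.** The strongest reply is that little is lost. The drug withdrawal is counted by dose in the overall TEAE table. The event has its SOC and PT in the general table, and also in the severity and relationship tables. With six active participants per cohort, one line of the AE listing joins the two. The one-to-one order of the section 11.1 list and the table numbers also suggests a word dropped from a title rather than a decision to count something else, and the shell states no derivation for the row. All of this stands, and it keeps the point minor.

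A reader might infer that the tables count study discontinuation only, so that a participant taken off drug vanishes from the summaries or an untolerated dose shows no discontinuations anywhere. The documents do not support that, because the drug-withdrawal row exists for both SAD and MAD.

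It is also fair to say that the illustrative case rests on withdrawal rules in a protocol that is not shown. If stopping drug for an AE always means early termination from the study, the two events coincide and the tables agree.

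On disposition, the slash in section 5 could be read as either treatment or study. But the sentence names both completion of and withdrawal from treatment/study, and the shells show only one of the two.

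What the reply does not remove is the contradiction itself. The SAP defines two events, its text asks for one by SOC and PT, and its shells deliver the other.

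**Conclusion.** The mismatch is real and minor. Section 11.1 and Tables 14.3.3.6.1/.2 describe different events by the SAP's own definitions, and section 5 and Tables 14.1.1.1/.2 differ in the same way. The effect is confined to two things: no table gives the SOC/PT of TEAEs that led to stopping drug, and no disposition table shows incomplete treatment.

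One affected MAD participant would be 16.7% of a cohort's active arm, or 5.6% of all active MAD participants. That figure is illustrative. It assumes the participant remains in the study after stopping drug, which the SAP allows for by its schedule but does not state. Nor should the point be stretched to say that a fed dose not given in cohort S3 must count as drug discontinuation. The SAP contains no such rule, and adding one would be a new definition rather than a correction.

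**What to change.** - **Tables 14.3.3.6.1 and 14.3.3.6.2:** change the title and header row to study-drug discontinuation in both the table list and the shells. State the derivation as action taken equal to drug withdrawn, as in Table 14.3.3.1.1. If study discontinuation by SOC and PT is also wanted, keep it as a separate, labelled block or table.
- **Tables 14.1.1.1 and 14.1.1.2:** add rows for treatment completed and treatment discontinued, with primary reason, beside the study-completion rows, so that the shells match section 5.

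The cost is two shell layouts, their MAD copies, the table-list titles and the related programs. Action taken is already in the AE listings, and doses not given are already listed with a reason in the study drug administration listings, so no new data are needed.
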